3. PLANNED ANALYSES

3.1. Final Analyses

The final planned analyses of the study will be performed after the completion of the following sequential steps (for this Clinical Data Interchange Standards Consortium [CDISC] study):

1. All subjects have completed the study as defined in the protocol.
2. All required database cleaning activities have been completed and final System Independent (SI) database release has been declared by Data Management (DM).
3. SI data to SDTM data conversion has completed by Conversion Service and quality control of unblinded SDTM has completed by DM.
4. All criteria for unblinding the randomization codes have been met.
5. Randomization codes have been distributed according to [RandAll NG].
6. Database freeze on SDTM datasets has been declared by DM

4. ANALYSIS POPULATIONS

Population	Definition / Criteria	Analyses Evaluated
All Subjects Enrolled (ASE)	
 • All subjects for whom a record exists in the study database, including screen failures and any subject who was not screened but experienced an SAE between the date of informed consent and the planned date of the Screening visit. 	
 • Subject Disposition • Reasons for withdrawal prior to randomisation • Inclusion, exclusion and randomisation criteria deviations • SAEs for non-randomised subjects
Intent-to-treat (ITT)	
 • All randomized subjects (excluding those who were randomized in error) who received at least one dose of study medication. A subject who is recorded as a screen or run-in failure and also randomized will be considered to be randomized in error. Any other subject who receives a randomization number will be considered to have been randomized. • Displays will be based on the treatment to which the subject was randomized 	
 • Study Population • Efficacy • Safety
Activity Monitoring (AM)	
 • All subjects in the ITT population who provide data from at least one activity monitoring session. • Displays will be based on the treatment to which the subject was randomized 	
 • Activity Monitoring

1. NOTE :

- Please refer to Section [10.8 Appendix 8: List of Data Displays](#) which details the population to be used for each display being generated.

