8. SAFETY ANALYSES

The safety analyses will be based on the ITT population, unless otherwise specified. Data collected after completion or withdrawal of study treatment will be considered post-treatment and included in relevant displays.

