10.4.2. Reporting Standards

General

 The current GSK Integrated Data Standards Library (IDSL) will be applied for reporting, unless otherwise stated (IDSL Standards Location: https://spope.gsk.com/sites/IDSLLibrary/SitePages/Home.aspx): 
 4.03 to 4.23: General Principles 5.01 to 5.08: Principles Related to Data Listings 6.01 to 6.11: Principles Related to Summary Tables 7.01 to 7.13: Principles Related to Graphics
Formats

 All data will be reported according to the randomised treatment the subject received unless otherwise stated. GSK IDSL Statistical Principles (5.03 & 6.06.3) for decimal places (DP's) will be adopted for reporting of data based on the raw data collected, unless otherwise stated. Numeric data will be reported at the precision collected on the eCRF. The reported precision from non eCRF sources will follow the IDSL statistical principles but may be adjusted to a clinically interpretable number of DP's. 
 FEV₁, FVC and IC will have a min and max to 2dp and then follow IDSL standards to reporting other summary statistics SGRQ and TDI will have a min and max to 1dp and then follow IDSL standards to reporting other summary statistics CAT will have a min and max to 0dp and then follow IDSL standards to reporting other summary statistics Odds Ratios and Hazard Ratios will be reported to 2dp

Planned and Actual Time	

 • Reporting for tables, figures and formal statistical analyses: 
 • Planned time relative to dosing will be used in figures, summaries, statistical analyses and calculation of any derived parameters, unless otherwise stated. Actual time will be used for calculation of times to events and Kaplan-Meier plots. • The impact of any major deviation from the planned assessment times and/or scheduled visit days on the analyses and interpretation of the results will be assessed as appropriate. • Reporting for Data Listings: 
 • Planned and actual time relative to study drug dosing will be shown in listings (Refer to IDSL Statistical Principle 5.05.1). • Unscheduled or unplanned readings will be presented within the subject's listings. 	
Unscheduled Visits	

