10.8.8. ICH Listings

ICH : Listings				
No.	Popu- lation	Title	Programming Note	Deliverable
Study Population				
1.	ITT	Listing of Subjects who Discontinued Study Treatment		SAC
2.	ITT	Listing of Reasons for Withdrawal		SAC
3.	ASE	Listings of Reasons for Withdrawal – Subjects Randomised but not in the Intent-to-Treat Population		SAC
4.	ITT	Listing of the Follow-up Contact		SAC
5.	ITT	Listing of Important Protocol Deviations		SAC
6.	ITT	Listing of Subjects with Inclusion, Exclusion or Randomisation Criteria Deviations		SAC
7.	ITT	Listing of Subjects for whom the Treatment Blind was Broken		SAC
8.	ITT	Listing of Randomised and Actual Treatments		SAC
9.	ITT	Listing of Overall Treatment Compliance		SAC
10.	ITT	Listing of Demographic Characteristics		SAC
11.	ITT	Listing of Race		SAC
12.	ITT	Listing of Medical Conditions		SAC

ICH : Listings				
No.	Popu- lation	Title	Programming Note	Deliverable
13.	ITT	Listing of Cardiovascular Risk Factors		SAC
14.	ITT	Listing of Family History of Cardiovascular Risk Factors		SAC
15.	ITT	Listing of Concomitant Medications Given for a COPD Exacerbation		SAC
16.	ITT	Listing of Concomitant Medications Not Given for a COPD Exacerbation		SAC
17.	ITT	Relationship between ATC Level 1, ingredient and verbatim text Non-COPD medications		SAC
18.	ITT	Listing of COPD History	Include COPD duration and COPD type	SAC
19.	ITT	Listing of Smoking History and Smoking Status		SAC
Study Population				
20.	ITT	Listing of Screening Lung Function Test Results		SAC
21.	ITT	Listing of GOLD Grade/Categories, Reversibility and long-acting bronchodilator usage stratum at Screening		SAC
22.	ITT	Listing of Derived FEV1 (L) Endpoints		SAC
23.	ITT	Listing of Derived FVC (L) Endpoints		SAC
24.	ITT	Listing of Derived IC (L) Endpoints		SAC

ICH : Listings				
No.	Popu- lation	Title	Programming Note	Deliverable
25.	ITT	Listing of Derived Rescue Use Endpoints (eDiary)		SAC
26.	ITT	Listing of Derived Rescue Use Endpoints (eMDI)		SAC
27.	ITT	Listing of Derived E-RS Scores		SAC
28.	ITT	Listing of CAT Scores	Include Screening	SAC
29.	ITT	Listing of SGRQ Scores		SAC
30.	ITT	Listing of TDI Scores		SAC
Exposure				
31.	ITT	Listing of Exposure		SAC
Adverse Events				
32.	ITT	Listing of Subject Numbers for Individual Adverse Events		SAC
33.	ITT	Listing of All Adverse Events		SAC
34.	ITT	Listing of Non-fatal Serious Adverse Events		SAC
35.	ITT	Listing of Fatal Serious Adverse Events		SAC

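### SAP Section 4 assigns SAEs in non-randomised subjects to the ASE population, but no SAE or death display uses it, and any dosed subject randomised in error falls outside every on-treatment safety display

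*SAP*

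**What the plan says.** Section 4 defines three populations: ASE, ITT and Activity Monitoring. None is a separate safety set.

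- ASE holds every subject with a database record. It even reaches a consented subject who had an SAE before being screened. Among its listed uses is "SAEs for non-randomised subjects".
- ITT is all dosed randomised subjects, "excluding those who were randomized in error". The exclusion is then defined: "A subject who is recorded as a screen or run-in failure and also randomized will be considered to be randomized in error". Taking study drug does not restore such a subject. Safety is listed among the uses of ITT, and for ITT, "Displays will be based on the treatment to which the subject was randomized".

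A note under the Section 4 table says that Appendix 8 gives the population for each display. Section 8 sets the default: "The safety analyses will be based on the ITT population, unless otherwise specified". Section 10.4.2 adds a general rule on arm: "All data will be reported according to the randomised treatment the subject received unless otherwise stated".

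**The concern.** ASE is drawn widely enough to catch serious events before or without randomisation, and Section 4 says it will be used for them. If no display in Appendix 8 does so, a programmer working from that appendix will not produce the output, and a serious or fatal event in a non-randomised subject will be missing from the SAE and death displays.

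The second issue is exposure. Excluding subjects randomised in error can be defended for efficacy. For safety, what matters is whether the subject took the drug. A default that removes dosed subjects because of an eligibility record could omit a serious or fatal event in someone who was treated. The point concerns what the study report displays, not whether the events are collected.

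**Working it through.** No sample size, power or error-rate figure bears on this. The check is a reading of the population column in Appendix 8 against the definitions in Section 4.

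**Step 1: all safety tables and figures, and the AE listings.**

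| Block | Displays | ITT | ASE |
|---|---|---|---|
| Main safety tables (3.01 to 3.22, and 3.33) | 23 | 21 | 2 (3.10, 3.16) |
| Safety figure 3.01 | 1 | 1 | 0 |
| Maintenance-naive safety tables (3.34 to 3.42) | 9 | 9 | 0 |
| AE listings 32 to 38 | 7 | 7 | 0 |

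Totals: 23 + 1 + 9 + 7 = 40 displays, of which 21 + 1 + 9 + 7 = 38 are ITT and 2 are ASE.

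**Step 2: displays devoted to SAEs.**

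- Main tables 3.06, 3.07, 3.08, 3.09, 3.11, 3.12, 3.15, 3.18 and 3.19: 9.
- Maintenance-naive tables 3.38, 3.39, 3.41 and 3.42: 4.
- Listings 34, 35 and 38: 3.

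9 + 4 + 3 = 16, all on ITT and none on ASE. The fatal-event listing ("Listing of Fatal Serious Adverse Events", number 35) is among them. The all-AE listing (33) and the all-cause deaths listing (56) are also ITT.

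**Step 3: follow an SAE in a non-randomised subject.** The subject is in ASE and not in ITT.

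- Table 3.06, the only table of pre-treatment SAEs, is ITT: not shown.
- Listings 33, 34, 35, 38 and 56 are ITT: not shown.
- Table 3.10 is ASE: the event is counted only if it led to withdrawal, and it is not marked as serious.
- Table 3.16 is ASE: the reported term appears against its coded term, and seriousness is not identified.

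Section 4 and Appendix 8 therefore contradict each other on this output.

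**Step 4: follow an on-treatment SAE in a dosed subject randomised in error.** The subject is again in ASE and not in ITT.

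- Every on-treatment AE and SAE table is ITT: not counted.
- Listings 32 to 38 and 56 are ITT: not listed.
- Table 3.10 covers pre-treatment events only. Table 3.16 carries the coded term.
- Listing 3 (ASE) covers randomised subjects outside ITT, but by its title gives only reasons for withdrawal.

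**The case against.** Much of the opposing case stands, and it limits how far the point goes.

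- A reader might infer that safety is shown only on ITT, or that these events appear nowhere. Tables 3.10 and 3.16 are on ASE, and the Section 8 rule is a default that allows exceptions. What is missing is any display that identifies the events as SAEs or deaths.
- A reader might infer that treated subjects' events are in fact being lost. The SAP does not say that any subject randomised in error was dosed. Listing 3 does not settle it, because a randomised subject can also be outside ITT by never taking a dose.
- A reader might infer that display by randomised arm loses events. It loses none. At most it can place an event under a product the subject did not take, and the plan makes that visible: Section 4.1 captures incorrect containers as important deviations, Listing 8 shows randomised and actual treatment, and Listing 57 shows misallocations. These listings cover ITT subjects only and do not change the tables. What remains is that the Section 10.4.2 wording can be read as either randomised or received treatment.
- A reader might take 3232 - 2424 = 808 from Section 2.3 as the size of the gap. That is an approximate planning count of screened subjects not randomised, not a number of SAEs. It also does not match ASE, which can include subjects who were never screened.

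None of this supplies the missing SAE display or brings a dosed subject outside ITT into an on-treatment display.

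**Conclusion.** The point holds in two parts. First, there is a definite inconsistency: Section 4 assigns SAEs in non-randomised subjects to ASE, and 0 of 16 SAE displays, and no death display, use ASE. Second, there is a conditional gap: for any dosed subject randomised in error, all AEs, SAEs and death fall outside the on-treatment safety tables and the AE, SAE and death listings.

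The number of subjects or events affected cannot be derived from the SAP. For dosed subjects randomised in error it may be zero. The conclusion assumes that Appendix 8 is followed as written, which Section 4 itself directs. No efficacy result is touched. The change should be made because it is cheap and the events at risk of omission include serious and fatal ones.

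**What to change.** 1. Put Listings 34, 35, 38 and 56 on ASE, or add ASE versions for subjects outside ITT, and add an ASE version of Table 3.06. Section 10.3.2 defines the pre-treatment phase by the treatment start date, so add a line covering subjects who were never dosed.
2. In Section 4, define a safety set of everyone who took any study drug, including those randomised in error. Use it for the exposure and on-treatment AE tables now on ITT and for Listings 32, 33, 36 and 37. At minimum, add an AE listing for dosed subjects outside ITT.
3. Leave Tables 3.10 and 3.16 on ASE: moving every safety table to a dosed-only set would remove the two that now reach non-randomised subjects. Keep efficacy, including the exacerbation displays, on ITT by randomised arm.
4. In Section 10.4.2, state whether safety displays use randomised or received treatment.

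The cost is SAP wording, one more population flag and a few display versions. The safety N may differ slightly from the ITT N, which a footnote can explain.

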4.1. Protocol Deviations

- Protocol deviations (PDs) will be tracked by the study team throughout the conduct of the study in accordance with the Protocol Deviation Management Plan (PDMP).
- Data will be reviewed by SDL prior to SDTM DBF to ensure all important deviations are captured and categorized on the protocol deviations dataset (except for the PD of taking incorrect treatment).
- Subjects who received an incorrect container will be captured as an important protocol deviation. Whether or not the incorrect container contains incorrect treatment will be identified following DBF in the Analysis Data Model (ADaM) dataset.
- Important protocol deviations (as identified in the PDMP) will be summarized and listed.
- A separate summary and listing of all inclusion/exclusion criteria deviations will also be provided. This summary will be based on data as recorded on the inclusion/exclusion page of the electronic case report form (eCRF).

5. CONSIDERATIONS FOR DATA ANALYSES AND DATA HANDLING CONVENTIONS

5.1. Study Treatment & Sub-group Display Descriptors

Treatment Group Descriptions			
RandAll NG		Data Displays for Reporting	
Code	Description	Description	Order in TFL
1	UMEC/VI 62.5/25 mcg once daily via ELLIPTA + placebo twice daily via DISKUS	UMEC/VI 62.5/25	1
2	UMEC 62.5 mcg once daily via ELLIPTA + placebo twice daily via DISKUS	UMEC 62.5	2
3	Salmeterol 50 mcg twice daily via DISKUS + placebo once daily via ELLIPTA	SAL 50	3

5.2. Baseline Definitions

For all endpoints (except as noted in baseline definitions) the baseline value will be the latest pre-dose assessment with a non-missing value, including those from unscheduled visits. If time is not collected, Day 1 assessments are assumed to be taken prior to first dose and used as baseline.

Endpoint	Baseline derivation
Trough FEV ₁ , FVC and IC	The mean of the values measured at 30 min and 5 min pre-dose on Day 1. If the actual time of an assessment is after the time of dosing on Day 1, the value at that assessment will be

Endpoint	Baseline derivation
	
set to missing prior to calculating baseline.
 
If one of the values is missing then the baseline will be the single remaining value; otherwise the baseline will be the mean of the two values.

TDI	
BDI assessment taken prior to dosing on Day 1.
 
The baseline dyspnea index (BDI) focal score will be calculated as the sum of the ratings recorded for each of the three individual scales (Functional Impairment, Magnitude of Task, Magnitude of Effort). Each of these scales has five possible scores ranging from 0 to 4 (with lower scores indicating more impairment), so the range of the BDI focal score is 0 to 12. If a score is missing (or has a value of W, X or Y) for any of the three scales, then the BDI focal score will be set to missing.

E-RS and subscale scores	Average of measurements from day -28 to day -1 inclusive; at least 16 days must be non-missing.
Physical activity	Average of measurements prior to randomisation; at least 3 days must be non-missing.
Rescue Use - Mean Number of Puffs of Rescue Medication Per Day and Percentage of Rescue-free Days Over Weeks 1-24 captured using e-diary	
The total puffs of rescue for each day will be calculated as number of salbutamol puffs. If the number of puffs is missing then the total puffs will be set to missing for that day.
 
The baseline number of inhalations is calculated using the mean number of total inhalations and the baseline percentage rescue use is calculated from the percentage of rescue free days as the average of measurements from day -28 to day -1 inclusive; at least 14 days must be non-missing.

Rescue Use - Mean Number of Occurrences of Rescue Medication Per Day and Percentage of Rescue-free Days Over Weeks 1-24 captured using e-MDI	
The total occurrences, defined as =>1 puff within a 2 minute time window, of rescue for each day will be calculated.
 
The baseline is calculated using the mean number of occurrences and the baseline percentage rescue use is calculated from the percentage of rescue free days as the average of measurements from the first date of sensor sync to the last date of sensor sync (per sensor subject combination) up until the day prior to first dose.

Unless otherwise stated, if baseline data is missing no derivation will be performed and baseline will be set to missing.

5.3. Multicentre Studies

- This study will be randomized centrally within country.
- It is likely that many centres will enrol a very small number of subjects and so rather than adjusting for centre in the statistical analyses, a geographical region will be used. This will consist of all centres within a similar geographical region.
- Country is determined by the location of the centre, as entered into GSK systems by the site monitor. The CENTREID variable will be used to identify and group centres.
- Geographical Region will be used wherever geographical region is included and defined as follows:

South America	North America	EU	Other
Argentina	Canada	France	Australia
Mexico	US	Germany	South Africa
		Italy	
		Netherlands	
		Spain	
		Sweden	

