2.3. Study Design

Overview of Key Study Design Features	
Design Features:	
 • Multi-centre, randomized, double blind, double dummy, 3-arm parallel group study to compare Umeclidinium/Vilanterol, Umeclidinium, and Salmeterol in subjects with chronic obstructive pulmonary disease (COPD). • Approximately 3232 subjects will be screened, such that 2424 subjects will be randomized and approximately 2181 evaluable subjects complete the study. • Eligible subjects will be stratified by country, long-acting bronchodilator usage during the run-in (none or one long-acting bronchodilator per day) and activity subset (activity subset or no activity subset), and randomized in a ratio of 1:1:1 to UMEC/VI inhalation powder (62.5/25 mcg once daily) administered via the ELLIPTA inhaler, or UMEC (62.5 mcg once daily) administered via the ELLIPTA or salmeterol (50 mcg BID) administered via the DISKUS. Note the activity subset was only included as a randomisation stratification group for logistical purposes. • A subset of subjects up to 150 per treatment arm will undergo assessment of their physical activity measured through a physical activity monitor (Actigraph GT9X) worn for 7 days from Screening (Visit 1), for 7 days from Randomisation (Visit 2), 7 days from Visit 3, and for 7 days prior to last clinic Visit (Visit 5). • The total duration of subject participation in the study will be approximately 29 to 35 weeks consisting of 6 weeks pre-screening if necessary, 4 weeks run-in, 24 week treatment and one week Follow-Up.
Dosing :	
 • The following study medications will be used in this study: 
 - UMEC/VI 62.5/ 25mcg administered via ELLIPTA - UMEC 62.5 mcg administered via ELLIPTA - Salmeterol 50 mcg administered via DISKUS - Placebo via ELLIPTA - Placebo via DISKUS 
Subjects will be instructed to take one dose of medication each morning from the ELLIPTA (one inhalation equals one dose), and one dose in the morning and one in the evening from the DISKUS.
 
The ELLIPTA will provide a total of 30 doses and the DISKUS will provide a total of 60 doses.

Overview of Key Study Design Features	

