Treatment Assignment:	
 • Subjects will be randomly assigned to one of the blinded study treatment regimens in equal proportion (ratio of 1:1:1): 
 - UMEC/VI 62.5/25 mcg once daily via ELLIPTA + placebo twice daily via DISKUS - UMEC 62.5 mcg once daily via ELLIPTA + placebo twice daily via DISKUS - Salmeterol 50 mcg twice daily via DISKUS + placebo once daily via ELLIPTA • GSK RandAll NG used to generate randomisation schedules. • Centralised randomisation within country using GSK RAMOS NG for treatment allocation. • Stratified by long-acting bronchodilator usage during run-in (none or one long-acting bronchodilator per day), country and activity subset (activity subset or no activity subset). Note the activity subset was only included as a randomisation stratification group for logistical purposes.
Interim Analysis	
 • No interim analysis will be performed.

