2.4. Statistical Hypotheses

The primary purpose of this study is to demonstrate improvements in lung function for subjects treated with UMEC/VI compared with UMEC for 24 weeks.

The primary endpoint is change from baseline in trough FEV₁ at Week 24.

The null hypothesis is no difference between treatment groups ($H_0: \mu_T - \mu_S = 0$), with the alternative hypothesis that there is a difference between treatment groups ($H_1: \mu_T - \mu_S \neq 0$), where μ_T is the mean change from baseline for UMEC/VI and μ_S is the mean change from baseline for UMEC.

In order to account for multiplicity across treatment comparisons and endpoints, a step-down closed testing procedure will be applied whereby inference for secondary endpoints or treatment comparisons are dependent upon statistical significance having been achieved for the primary comparison. If the primary comparison is significant i.e. the associated p-value for UMEC/VI versus UMEC for change from baseline in trough FEV₁ at Week 24 is below 0.05, this will allow inference of treatment comparisons (UMEC/VI versus UMEC on all secondary endpoints, and UMEC/VI versus Salmeterol and UMEC versus Salmeterol on all primary and secondary endpoints), which will be declared statistically significant if the associated p-value is below 0.05.

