7.1.5.1. Statistical Methodology Specification

Primary Statistical Analysis
Endpoint

 • Change from Baseline in trough FEV₁ at Week 24 (results for trough FEV₁ at all other time points and other treatment comparisons will be obtained from the same analysis even though those are not the primary endpoint)
Model Specification

 • Trough FEV₁ at Week 24 will be analysed for the ITT population using a mixed model repeated measures (MMRM) including data recorded at each of Week 4, Week 12 and Week 24. • The following covariates will be included in the model: baseline FEV₁, geographical region, stratum (no. of bronchodilators per day during run-in), visit, treatment, visit by baseline and visit by treatment interactions, where visit is nominal. • Two models will be fitted; one with a response variable of trough FEV₁, and one with a response variable of change from baseline in trough FEV₁. • While missing data are not explicitly imputed in the primary MMRM analyses, there is an underlying assumption that the data are missing at random. • The Kenward and Roger method (KR) for approximating the denominator degrees of freedom and correcting for bias in the estimated variance-covariance of the fixed effects will be used. • In the event the model fails to run using the KR method, then the residual method will be used instead. • An unstructured covariance structure for the R matrix will be used by specifying 'type='UN' on the REPEATED line. • Results for all time points where data are scheduled to be collected and all treatment comparisons will be included in the analysis and presented in the displays.
Model Checking & Diagnostics

 • Model assumptions will be applied but appropriate adjustments may be made based on the data.

Primary Statistical Analysis

- Normality assumptions underlying the model used for analysis will be examined by obtaining a normal probability plot of the residuals and a plot of the residuals versus the fitted values (i.e. checking the normality assumption and constant variance assumption of the model respectively) to gain confidence that the model assumptions are reasonable.
- If there are any departures from the distributional assumptions, alternative models will be explored using appropriately transformed data.

Model Results Presentation

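### Country is a randomisation stratum, but the linear models adjust only for four pooled regions, for a reason that does not reach country; any effect is a slightly conservative standard error

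*SAP*

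**What the plan says.** SAP Section 2.3 makes country a stratum: "Eligible subjects will be stratified by country, long-acting bronchodilator usage during the run-in", alongside the activity subset. Under treatment assignment it adds: "Centralised randomisation within country using GSK RAMOS NG for treatment allocation". Section 5.3 repeats that randomisation is central within country.

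For the analysis, Section 5.3 expects many small centres and concludes that "rather than adjusting for centre in the statistical analyses, a geographical region will be used". It describes the grouping thus: "This will consist of all centres within a similar geographical region". Its table puts 12 countries into four regions: South America (Argentina, Mexico), North America (Canada, US), EU (six countries) and Other (Australia, South Africa).

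The primary MMRM in Section 7.1.5.1 takes baseline FEV1 and then "geographical region, stratum (no. of bronchodilators per day during run-in), visit, treatment, visit by baseline", with a visit-by-treatment term. Section 7.2.5.1 carries the same structure to TDI, E-RS, SGRQ-C, CAT, eDiary rescue use, the log FEV1 ratio, FVC and IC. No model in Section 7 contains country.

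The three strata are handled differently. Section 5.4.1 brings bronchodilator use into the models because it is a stratum. Section 2.3 explains the activity subset as a logistical stratum. Country is replaced by a coarser factor without comment.

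**The concern.** When allocation is balanced within country, differences between countries largely cancel from the treatment contrast. A linear model that leaves country out still counts those differences as residual noise, so it reports a standard error larger than the true sampling variability of the estimate. Confidence intervals are then somewhat too wide and tests slightly conservative.

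The reason given for pooling is sparseness of centres. It does not carry over to country, the level at which the trial allocates. What is at stake is modest: an analysis that does not follow the design, in the primary MMRM and the continuous secondary MMRMs, when the matching covariate is already held for every centre.

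**Working it through.** **Inputs from the SAP**
- Strata and allocation within country: Section 2.3. Ratio: "randomized in a ratio of 1:1:1".
- Size: "2424 subjects will be randomized and approximately 2181 evaluable subjects complete the study" (Section 2.3). Per arm this is 2424/3 = 808 randomised and 2181/3 = 727 evaluable.
- Level: two-sided 5%. Section 2.4 sets 0.05 for the primary comparison and the same threshold for the dependent comparisons, "which will be declared statistically significant if the associated p-value is below 0.05".
- Countries: 2 + 2 + 6 + 2 = 12 (Section 5.3).

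**The plan's own figures.** 2181/(1 - 0.10) = 2423.3, which rounds up to 2424. The two counts therefore agree with 10% loss, although the SAP does not state that percentage. It states no SD, effect size or power, so no planned standard error or power can be reproduced.

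**Size of the strata.** 2424/12 = 202 subjects per country on average. This is not a country count; the SAP gives none. Country uses 12 - 1 = 11 parameters and region 4 - 1 = 3, a difference of 8.

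**Effect on the standard error.** Each country lies in exactly one region, so the region term removes all between-region differences. Let r be the share of the remaining residual variance that lies between countries of the same region, s² the total residual variance, and n the number per arm.
- Variance reported by the region model: 2s²/n.
- True variance when arms are balanced within country: 2s²(1 - r)/n.
- Reported SE / true SE = 1/sqrt(1 - r); n cancels.
- Actual two-sided alpha = 2 × (1 - Φ(1.96/sqrt(1 - r))).
- Power of a test that would have 90% power with the true SE (an illustration, as the SAP states no power) = Φ(1.960 + 1.282 - 1.960/sqrt(1 - r)).

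The SAP does not give r, so these values are assumed:

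| r | SE ratio | Actual alpha | Power (90% with true SE) |
|---|---|---|---|
| 0 | 1.000 | 5.0% | 90.00% |
| 1% | 1.005 | 4.9% | 89.83% |
| 2% | 1.010 | 4.8% | 89.65% |
| 5% | 1.026 | 4.4% | 89.08% |
| 10% | 1.054 | 3.9% | 88.01% |

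**Check by simulation.** The set-up had 2424 subjects, three arms, 12 countries of assumed unequal size in the SAP's four regions, blocks of an assumed size 6 within country and bronchodilator stratum, a single-visit linear model, and 3000 runs for each r.
- Region in the model: reported over empirical SE was 0.99, 1.01, 1.03 and 1.06 at r = 0, 2%, 5% and 10%; type I error was 5.2%, 4.3%, 4.4% and 4.1%.
- Country in the model: the ratio stayed at 0.99 to 1.01 and type I error at 4.6% to 5.2%.

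The Monte Carlo error of a 5% rate is sqrt(0.05 × 0.95/3000) = 0.4 percentage points, so the simulation agrees with the formula.

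**The case against.** Region is pre-specified and is a common covariate choice, and the consequence is conservative. If countries within a region do not differ after adjustment, r is zero and nothing is lost. The models adjust for baseline and visit by baseline, which should take up much of any stable country or language shift. An average of 202 says nothing about the smallest country, and the protocol, not shown here, may give a reason. All of this limits the size of the point. None of it supplies a reason for passing over country, and Table 1 of the SAP (Section 2.1) records no change on this matter.

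Stronger readings are tempting, but the document does not support them:
- A reader might infer that every model is affected. The physical activity MMRM in Section 7.3.5.1 has no region term. In the Cox, negative binomial and GLIMMIX models, leaving out a prognostic factor can also change the effect being estimated, so the standard-error argument does not carry over.
- A reader might infer that the country stratification is ignored. Region recovers the between-region part; only the within-region part is left out.
- A reader might infer that standard errors are known to be too wide, or that precision worth some number of subjects is lost. The first depends on r, which the SAP does not give. On the second, the estimate keeps the precision that the design gives it; only the reported standard error is conservative.
- A reader might infer that the regions as a whole break the rule in Section 5.3. Six European countries are plainly a similar region, and a residual level called Other is conventional. Mexico under South America is a real but minor slip.

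**Conclusion.** The point holds as a minor one. Country is a randomisation stratum, the primary MMRM and the continuous secondary MMRMs use a coarser region, and the stated reason does not cover country. In these linear models the reported standard error can be conservative: by at most about 2.6% for r up to 5%, and by 5.4% at r = 10%, with actual alpha of about 4.4% and 3.9% respectively. Type I error is not inflated. For FEV1 the effect is probably near the lower end of the range because the model adjusts for baseline.

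This rests on an assumed r and on arms staying close to balance within country among the subjects analysed. It gives no ground to doubt the validity of the primary comparison.

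**What to change.** - In Sections 5.3, 5.4.1 and 7.1.5.1, name country as a randomisation stratum and use it (12 levels) in place of geographical region in the primary MMRM. Carry this to the MMRMs for the continuous secondary endpoints in Section 7.2.5.1.
- Pre-specify, before unblinding, a rule for pooling any very small country, stating the size threshold and the country it joins.
- Keep region for the treatment-by-region interaction and for the sparse-event models.
- In the Section 5.3 table, move Mexico or rename the level so that label and content agree.

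The cost is SAP wording, one covariate in the model code and eight more model parameters against more than 2000 subjects. No new data are needed: Section 5.3 already derives country from each centre's location, and Tables 1.6 and 1.29 already report by country.
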